8.4	STATISTICAL METHODS	21
8.4.1	Data Analysis	21
8.4.2	Univariate Analysis	21
8.4.3	Analysis of Treatment Assignment and Outcome Measures	22
8.4.4	Survival Analysis	22
8.4.5	Missing Data and Dropouts	22
8.5	INTERIM MONITORING GUIDELINES	22
8.6	PROTOCOL VIOLATIONS.....	22
8.7	SAFETY ANALYSIS	23
9	PARTICIPANT SAFETY, ADVERSE EVENTS, AND CONFIDENTIALITY	23
9.1	CONSENT	23
9.2	INSTITUTIONAL REVIEW BOARD PROCESS	23
9.3	SAFETY AND ADVERSE EVENTS	23
9.3.1	Definitions	23
9.3.2	Classifying Adverse Events	25
9.3.3	Interpretation of Definitions	26
9.3.4	Reporting Procedures for Unanticipated Problems and Adverse Events	27
9.4	SUBJECT WITHDRAWAL	29
9.5	UNMASKING/UNBLINDING PROCEDURES	30
9.6	MEDICAL MONITORING	30
9.6.1	Internal Data and Safety Monitoring Board	31
9.7	CONFIDENTIALITY OF STUDY DATA.....	31
10	QUALITY CONTROL AND DATA HANDLING.....	31
10.1	PERSONNEL TRAINING	31
10.2	DATA QUALITY.....	31
10.3	SOURCE DOCUMENTS	32
10.4	CASE REPORT FORMS	32
10.5	DATA MANAGEMENT.....	32

10.6	AUDIT AND INSPECTION	33
10.7	ARCHIVING	33
10.8	RECORDS RETENTION	33
11	ETHICAL CONSIDERATIONS.....	33
12	STUDY FINANCES.....	34
12.1	FUNDING SOURCE	34
13	REFERENCES.....	34

LIST OF ABBREVIATIONS

AE	Adverse Event/Adverse Experience
CCC	Clinical Coordinating Center
CFR	Code of Federal Regulations
CRF	Case Report Form
DSMB	Data and Safety Monitoring Board
FDA	Food and Drug Administration
GCP	Good Clinical Practice
HIPAA	Health Insurance Portability and Accountability Act
IB	Investigator's Brochure
ICF	Informed consent form
IND	Investigational New Drug Application
IRB	Institutional Review Board
PHI	Protected Health Information
PI	Principal Investigator
SAE	Serious Adverse Event/Serious Adverse Experience
SOP	Standard Operating Procedure
TLC	Total Lung Capacity
TTE	Transthoracic echocardiography

Study Summary

Title	Letrozole in Patients with Hepatopulmonary Syndrome: A Double-Blind Randomized Clinical Trial
Running Title	Letrozole in HPS
Protocol Number	19-005779
Phase	Phase II
Methodology	Open label
Overall Study Duration	1 year
Subject Participation Duration	6 months
Single or Multi-Site	Multi-Site
Objectives	
Primary Aim:
 
 • To determine whether letrozole affects alveolar-arterial oxygen gradient (AaPO₂) at 6 months in patients with HPS 
Secondary Aims:
 
 • To determine whether letrozole affects estradiol, progesterone, testosterone levels at 6 months • To determine whether letrozole affects SF-36 questionnaire scores and mMRC dyspnea scale at 6 months • To determine whether letrozole affects the distance walked in six minutes at 6 months • To determine whether letrozole affects AaPO₂ and PaO₂ at 3 months and 6 months in patients with HPS • To determine whether letrozole affects oxygen saturation from pulse oximetry at 3 months 6 months in patients with HPS • To determine the safety and side effects associated with letrozole administration in patients with HPS
Indication	Hepatopulmonary syndrome

Diagnosis and Main Inclusion Criteria	
Inclusion Criteria
 
 - Diagnosis of moderate to very severe hepatopulmonary syndrome: 
 o Presence of liver disease or portal hypertension o Intrapulmonary shunting on contrast-enhanced echocardiogram o Hypoxemia [A-a gradient ≥ 15 mmHg (or ≥ 20 mmHg if age >64) and $\text{PaO}_2 < 80$ mmHg on arterial blood gas testing] - Child-Pugh class A or B liver disease - MELD score < 20 - ≥ 18 years old - Female subjects must be post-menopausal (defined as 12 months of spontaneous amenorrhea or 6 weeks postsurgical bilateral oophorectomy without or without hysterectomy) - Ability to provide informed consent 
Exclusion Criteria
 
 - Enrollment in a clinical trial or concurrent use of another investigational drug or device therapy (i.e., outside of study treatment) during, or within 28 days of baseline - Current hepatic encephalopathy - Expectation of liver transplant within six months of randomization - - Concomitant lung disease defined as restriction ($\text{TLC} < 70\%$) or obstruction ($\text{FEV}_1 < 80\%$ & $\text{FEV}_1/\text{FVC} < 70\%$) - Inability to comply with the study protocol - Osteoporosis - Premenopausal women (those who have not reached 1 year absence of menarche) - Vulnerable study population, including imprisoned individuals, or those who cannot consent on their own.
Study Design	Randomized, double-blind, placebo-controlled parallel trial of 20 subjects with HPS. Eligible subjects will be randomly assigned 1:1 to receive either letrozole 2.5 mg orally daily or placebo for 6 months.
Number of Subjects	20 total subjects; 10 subjects at each site
Duration of Administration	6 months
Reference therapy	There is no reference therapy

Statistical Methodology	
Primary endpoint:
 
 • Difference in changes in AaPO₂ between letrozole and placebo groups at 6 months. 
Secondary endpoints:
 
 • Difference in changes in intrapulmonary shunting between letrozole and placebo groups at 6 months • Difference in changes in estradiol, progesterone, testosterone levels between letrozole and placebo groups at 3 months and 6 months • Difference in changes in SF36 scores and mMRC dyspnea scale scores between letrozole and placebo groups at 6 months • Difference in changes in distance walked in six minutes between letrozole and placebo groups at 6 months • Difference in changes in PaO₂ and oxygen saturation by pulse oximetry between letrozole and placebo groups at 3 months and 6 months • To assess the effect of letrozole versus placebo on AaPO₂ at 3 months and 6 months • Safety and side effects associated with letrozole administration in patients with HPS 
Sample size and power:
 
A total of 20 patients will be enrolled (10 letrozole, 10 placebo), which will provide 80% power to detect a 13.2 mm Hg difference in changes in AaPO₂ ($\alpha = 0.05$).
 
Data analysis:
 
The primary analysis will compare the absolute change from baseline to 6 months in AaPO₂ between the blinded treatment arms using a two-sample t-test. Incidence of adverse events and secondary endpoints will also be analyzed.

-------------------------	---

1 Introduction

This document is a protocol for a human research study. This study will be carried out in accordance with the applicable United States government regulations as well as research policies and procedures of both Mayo Clinic and the University of California, San Francisco.

1.1 Background

Hepatopulmonary syndrome is common among liver transplant candidates and is associated with increased mortality. Hepatopulmonary syndrome (HPS) is characterized by the triad of liver disease, intrapulmonary vascular dilatation (IPVD), and abnormal arterial oxygenation [Alveolar-arterial (A-a) gradient ≥ 15 mmHg, or ≥ 20 mmHg if age > 64](1). Among the nearly 3 million Americans living with cirrhotic disease, 5-30% have HPS and this alone is associated with a worse quality of life and twice the already significantly elevated risk of death in this patient population (1, 2). The main pathophysiologic finding in HPS is abnormal intrapulmonary vasodilation which leads to a ventilation-perfusion (V-Q) mismatch, limited diffusion, and shunting. All this manifests as hypoxemia in patients affected by this disease.

There are currently no effective medical therapies for HPS. Animal models of HPS have been important in elucidating the pathogenesis of this disease but have not translated to effective medical therapies for this population. Many treatments have been trialed without significant benefit – somatostatin, almitrine, indomethacin, norfloxacin, inhaled L-NAME, pentoxifylline, and aspirin to name a few (1). While small studies have shown a modest improvement in oxygenation with garlic extract and intravenous methylene blue, use of these agents has not been adopted or recommended clinically(3).

Currently, the only curative therapy for HPS is liver transplantation. While severity of liver disease does not correlate with severity of HPS, transplantation results in resolution of hypoxemia in the majority of patients. Thus, cirrhosis with severe hypoxemia (defined as partial pressure of oxygen (PaO_2) <60 mmHg) is an indication for liver transplant. Once the hypoxemia progresses, however, to $\text{PaO}_2 <45$ mm Hg, there is a significantly increased risk of complications post-transplantation and higher mortality (1, 4). Patients with HPS are eligible to receive a Model for End Stage Liver Disease (MELD) exception points, or waitlist priority upgrade, in order to expedite transplantation and allow for transplantation at a less severe stage of disease progression (5). Between 2002 and 2012, nearly 1,000 patients received HPS MELD exception points and 739 underwent liver transplant (4). Effective medical therapies for patients with HPS could allow these organs to be allocated to patients with more severe liver disease and higher native MELD scores.

Animal and human studies have shown increased levels of circulating estrogen to be associated with pulmonary vasodilation and vascular remodeling. Many studies, especially in the realm of pulmonary arterial hypertension (PAH), have not only shown this association but also suggested a benefit from decreasing levels of circulating estrogen in this population using aromatase inhibition. As estrogen is metabolized in the liver, patients with cirrhosis have elevated levels of circulating hormone which could contribute to changes in pulmonary vasculature and function (6-10).

Letrozole is an aromatase inhibitor which blocks the peripheral conversion of testosterone to estrogen. We will perform a Phase II randomized, double-blind, placebo-controlled parallel

trial in 20 subjects with HPS to determine the effect of 6 months of treatment with letrozole 2.5 mg daily on the alveolar-arterial (A-a) gradient.

1.2 Investigational Agent

Letrozole, an oral aromatase inhibitor, is a commercially available agent which works to inhibit the conversion of androgens to estrogen. Letrozole is FDA-approved as adjuvant treatment of early breast cancer in postmenopausal women with hormone receptor positive tumors; as extended adjuvant treatment of early breast cancer in postmenopausal women who have received 5 years of tamoxifen; and as a first or second line treatment of advanced breast cancer in postmenopausal women with locally advanced or metastatic disease.

1.3 Dose Rationale

The rationale for the dose is based on typical dose regimens for other conditions (breast cancer adjuvant or primary treatment). Letrozole is only available orally. Letrozole has a half-life of 2 days and in prior pharmacokinetic studies a dose of 2.5 mg daily takes from 2-6 weeks to reach steady-state plasma concentrations.

1.4 Risks and Benefits

The most frequent adverse reactions seen in controlled trials of letrozole were:

Common

- **Cardiovascular:** Edema (7.2% to 18.4%)
- **Dermatologic:** Hot sweats (6% to 49.7%), Sweating (Up to 24.2%)
- **Endocrine metabolic:** Hypercholesterolemia (52.3%)
- **Gastrointestinal:** Constipation (1.5% to 11.3%), Diarrhea (5% to 8%), Loss of appetite (3% to 5%), Nausea (8.6% to 17%), Vomiting (2.7% to 7%)
- **Musculoskeletal:** Arthralgia (8% to 48.2%), Arthritis (6.7% to 21.1%), Backache (5% to 18%), Bone pain (22%), Myalgia (6.7% to 11.4%)
- **Neurologic:** Asthenia (4% to 33.6%), Dizziness (2.4% to 14.2%), Headache (3.5% to 20.1%), Insomnia (5.8% to 7%), Somnolence (2% to 3%)
- **Respiratory:** Dyspnea (5.5% to 18%)
- **Other:** Fatigue (9.6% to 16.8%)
-

Serious

- **Cardiovascular:** Heart failure, Myocardial infarction (0.4%)
- **Hematologic:** Pancytopenia, Thromboembolic disorder (1.1%)
- **Musculoskeletal:** Decreased bone mineral density (3.8% to 4.1%), Fracture of bone (5.9% to 14.7%)
- **Respiratory:** Pleural effusion (Less than 5%), Pulmonary embolism (2% or less)

Since there are no approved or available medical therapies for HPS and since HPS is associated with increased mortality, the risks of letrozole use are reasonable and are outweighed by the benefits. Additionally, we will exclude patients with baseline osteoporosis in order to minimize the risk of further loss of bone mineral density and/or fracture.

2 Study Objectives

Primary Aim:

- To determine whether letrozole affects alveolar-arterial oxygen gradient (AaPO₂) at 6 months in patients with HPS.

Secondary Aims:

- To determine whether letrozole affects estradiol, progesterone, testosterone levels at 6 months
- To determine whether letrozole affects SF-36 questionnaire scores and mMRC dyspnea scale at 6 months
- To determine whether letrozole affects the distance walked in six minutes at 6 months
- To determine whether letrozole affects AaPO₂ and PaO₂ at 3 months and 6 months in patients with HPS
- To determine whether letrozole affects oxygen saturation from pulse oximetry at 3 months and 6 months in patients with HPS
- To determine the safety and side effects associated with letrozole administration in patients with HPS

3 Study Design

3.1 General Description

This study is a phase II randomized, double-blind, placebo-controlled parallel trial of 20 subjects with hepatopulmonary syndrome designed to assess the effect of letrozole 2.5 mg orally daily or placebo for 6 months on the alveolar-arterial oxygen gradient (AaPO₂).

Subjects at each site will be screened at outpatient clinic visit appointments and interested qualified subjects will be consented and offered participation in this trial. Once consent has been obtained baseline values will be established and subjects will begin letrozole with follow-up clinic visits and testing at 1 month, 3 months, and 6 months.

3.2 Number of Subjects

A total of 20 subjects will be enrolled. Each site will enroll 10 patients.

3.3 Duration of Participation

Subjects will participate for 6 months.

3.4 Primary Study Endpoints

- Primary endpoint: Difference in changes in AaPO₂ between letrozole and placebo groups at 6 months

3.5 Secondary Study Endpoints

- Secondary Endpoints:
 - o Difference in changes in intrapulmonary shunting between letrozole and placebo groups at 6 months
 - o Difference in changes in estradiol, progesterone, testosterone levels between letrozole and placebo groups at 3 months and 6 months
 - o Difference in changes in SF36 scores and mMRC dyspnea scale scores between letrozole and placebo groups at 6 months
 - o Difference in changes in distance walked in six minutes between letrozole and placebo groups at 6 months
 - o Difference in changes in PaO₂ and oxygen saturation by pulse oximetry between letrozole and placebo groups at 3 months and 6 months
 - o To assess the effect of letrozole versus placebo on AaPO₂ at 3 months and 6 months
 - o Safety and side effects associated with letrozole administration in patients with HPS
 - o Change in upright A-a gradient from baseline to 6 month follow-up

3.6 Identification of Subjects

Ten subjects with HPS will be recruited at Mayo Clinic - Rochester, and the University of California - San Francisco, and randomized to either letrozole or placebo in a double-blind fashion. Patients will be identified by the medical staff in the liver and pulmonary clinics and liver transplant programs.

For screening, we will perform computerized searches at the sites for patients with an ICD-9 or ICD-10 code for HPS (573.5 or K76.81) or with late shunting by contrast echo with an abnormal arterial blood gas (ABG).

We expect to screen approximately 35 patients (primarily new evaluations for liver transplant and those already listed for transplant) over approximately 1 year between the two centers. Of these, we expect approximately 85.7% (n=30) to meet inclusion/exclusion criteria. Using our current study numbers as a guide, we expect approximately 20 patients to consent and be eligible for randomization.

4 Subject Selection Enrollment and Withdrawal

4.1 Inclusion Criteria

- ≥ 18 years old
- Diagnosis of moderate to very severe hepatopulmonary syndrome:
 - o Presence of liver disease or portal hypertension
 - o Intrapulmonary shunting on contrast-enhanced echocardiogram
 - o Hypoxemia [A-a gradient ≥ 15 mmHg (or ≥ 20 mmHg if age > 64) and PaO₂ < 80 mmHg on arterial blood gas testing]
- Child-Pugh class A or B liver disease
- MELD score < 20

- ≥ 18 years old
- Female subjects must be post-menopausal (defined as 12 months of spontaneous amenorrhea or 6 weeks postsurgical bilateral oophorectomy without or without hysterectomy)
- Ability to provide informed consent

4.2 Exclusion Criteria

- Enrollment in a clinical trial or concurrent use of another investigational drug or device therapy (i.e., outside of study treatment) during, or within 28 days of baseline
- Current hepatic encephalopathy
- Expectation of liver transplant within six months of randomization
-
- Concomitant lung disease defined as restriction (TLC < 70%) or obstruction (FEV1 < - 80% & FEV1/FVC < 70%)
- Inability to comply with the study protocol
- Osteoporosis
- Premenopausal women (those who have not reached 1 year absence of menarche)
- Vulnerable study population, including imprisoned individuals, or those who cannot consent on their own.

4.3 Subject Recruitment, Enrollment and Screening

Patients with HPS will be identified by clinical providers and co-investigators who provide clinical care for patients with HPS. Study personnel (study coordinator, principal investigator or co-investigator) will approach potential participants in the outpatient setting (Liver transplant clinic or pulmonary clinic) or inpatient setting for recruitment and study participation. Patients may also be contacted by telephone prior to or following their clinic visit for recruitment. The telephone script used for recruitment is attached in the IRB protocol.

4.4 Randomization

Randomization will be blocked to ensure balance over time. The Research Pharmacy at Mayo Clinic and the University of California, San Francisco will prepare the prescriptions.. At the baseline visit, when the research coordinator registers the patient as meeting all inclusion/exclusion criteria, the patient can pick up that medication at the Research Pharmacy .

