- Modified Medical Research Council (mMRC) Dyspnea Scale assessment Values can be obtained from last 30 days.

- SF-36 questionnaire assessment
- 6 minute walk distance with Borg Score
- Dispense supply of study drug
- Reinforce instructions on recording of new medications and dose changes
- Reinforce instructions on bringing the subject's routine and study medications to all visits

Blood samples for study assays will be processed and/or banked.

After confirming inclusion criteria, the subject will be randomized to a treatment group using the Web-based database by the research coordinator. A pre-packaged 3 month supply of study medication (encapsulated letrozole 2.5 mg or placebo capsules) will be dispensed by the Research Pharmacy. Subjects will be instructed on the proper administration of the study medication.

Once instruction has been given to the subject and the subject expresses understanding, the research coordinator will thank the subject for their attendance and reinforce compliance with the study medication and protocol. The subject is encouraged to update their primary doctor about their medication changes.

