8.4 Statistical Methods

8.4.1 Data Analysis

The intent-to-treat analysis will include all randomized subjects. Hypothesis testing will use two-sided α level 0.05 without correction for multiplicity. We will summarize demographics and baseline and follow-up endpoints.

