8.4.3 Analysis of Treatment Assignment and Outcome Measures

The primary analysis will compare the absolute change from baseline to 6 months in AaPO2 between the blinded treatment arms using a two-sample t-test. This will be supplemented with mixed analysis of variance methods to allow inclusion of the baseline value (fixed) and clinical site (random). If the data are not normally distributed, they will be transformed. For dichotomous outcomes, logistic regression will be used. For secondary outcomes with additional longitudinal assessments, including results of the plasma biomarker assessments, 6MWT, SF-36, ABG, and the modified Medical Research Council Dyspnea Scale, linear mixed effects models or generalized estimating equations will be used as appropriate. All patients will be assessed for toxicity and included in the safety analysis. This analysis will include summaries of the incidence and grade of toxicities. Patients will be evaluated for serious adverse events. Safety interim analyses will be performed and reported at each continuing review with the IRB.

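### Blocking is specified over time but stratification by site is not stated, and the primary t-test has no site term, so a chance site imbalance would go uncorrected in a 20-patient trial

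*Combined protocol and SAP*

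**What the plan says.** On allocation, the combined protocol and SAP states in section 4.4: "Randomization will be blocked to ensure balance over time". The Study Summary gives the ratio: "Eligible subjects will be randomly assigned 1:1 to receive either letrozole 2.5 mg orally daily or placebo for 6 months". No section names a stratification factor or a block size, or says whether there is one list or one per site. Two further statements bear on this without settling it. Section 6.1.1, in the baseline visit text, says that "the subject will be randomized to a treatment group using the Web-based database by the research coordinator". Section 4.4 adds: "The Research Pharmacy at Mayo Clinic and the University of California, San Francisco will prepare the prescriptions".

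On sites, section 3.2 says: "Each site will enroll 10 patients". The Study Summary plans 10 patients per arm, 20 in total.

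On analysis, section 8.4.3 compares the absolute change in AaPO2 from baseline to 6 months "between the blinded treatment arms using a two-sample t-test". The following sentence adds, as a supplement, a mixed model with the baseline value as fixed and clinical site as random. Section 8.4.5 plans a completers analysis for the primary endpoint. The power statement in section 8.2 contains no site term.

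**The concern.** Blocking in calendar order keeps the arms level over time. It does not keep them level within a site unless the blocks are formed within site. With 10 patients per site, an uneven split is common under a shared list. If the sites also differ in how AaPO2 changes over six months, part of that difference is read as a treatment effect, because the primary test has no term to remove it.

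Only a site difference in change matters; a stable difference in level cancels in the change score. The text leaves room for a difference in change. Section 6.1.1 lets the baseline blood gas come from the previous 90 days, while section 6.3 takes the six-month value at a visit with a 30-day window either side. Two sites could use these allowances differently. The supplementary model suggests that the authors thought site might matter, but neither the stated allocation rule nor the primary test protects against it.

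**Working it through.** **Inputs.** From the documents: 20 patients, 10 per arm (Study Summary); 10 per site (3.2); SD of change about 10 mmHg, 80% power, 13.2 mmHg (8.2); two-sided 0.05 (8.4.1). Assumed: D, the site difference in mean change, which the documents do not give, taken as 2.5, 5 or 10 mmHg for the shifts and 0, 5 or 10 in the simulation; and the SD of 10 read as the within-site SD.

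**Step 1: the plan's own figure.** SE = 10 × √(1/10 + 1/10) = 4.47 mmHg; 13.2 / 4.47 = 2.95. The exact noncentral-t power with 18 df is 79.7% (exactly 80% at 13.25 mmHg). The stated 80% is reproduced.

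**Step 2: how often a shared list splits unevenly.** With 10:10 overall and 10 per site, the number a on letrozole at one site is hypergeometric: P(a) = C(10,a)² / C(20,10), with C(20,10) = 184,756. The letrozole arm draws a/10 of its patients from that site and placebo (10 − a)/10, so the unadjusted difference shifts by D × (2a − 10)/10.

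| Split at a site | Probability, either direction | Shift |
|---|---|---|
| 5:5 | 252² / 184,756 = 34.4% | 0 |
| 6:4 | 2 × 210² / 184,756 = 47.7% | 0.2D |
| 7:3 | 2 × 120² / 184,756 = 15.6% | 0.4D |
| 8:2 | 2 × 45² / 184,756 = 2.2% | 0.6D |
| 9:1 | 2 × 10² / 184,756 = 0.1% | 0.8D |

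So 6:4 or worse has probability 65.6%, 7:3 or worse 17.9%, and 8:2 or worse 2.3%. Simulated shared lists with block sizes 2, 4, 10 and 20 and sites interleaved at random gave 17.9% to 18.3% for 7:3 or worse. Blocking over time therefore does not remove the risk.

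**Step 3: size of the shift.** At 7:3, 0.4D is 1, 2 or 4 mmHg for D = 2.5, 5 or 10, which is 8%, 15% or 30% of 13.2. The mean absolute shift is 0.477 × 0.2 + 0.156 × 0.4 + 0.022 × 0.6 + 0.001 × 0.8 = 0.17D, or 0.4, 0.9 or 1.7 mmHg.

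**Step 4: error rates.** Simulation with 20,000 runs per case. Each cell shows type I error / power at 13.2 mmHg. The site term is a fixed factor with 17 df.

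| D | Shared list, t-test | Shared list, site term | Stratified, t-test | Stratified, site term |
|---|---|---|---|---|
| 0 | 4.9% / 79% | 5.0% / 76% | 5.0% / 80% | 5.0% / 79% |
| 5 | 5.0% / 77% | 5.1% / 77% | 4.6% / 78% | 5.3% / 80% |
| 10 | 4.8% / 70% | 5.0% / 77% | 2.8% / 72% | 4.9% / 79% |

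Given a 7:3 or worse split under a shared list, the t-test's type I error is about 7% at D = 5 and 10% to 11% at D = 10. Its power at 13.2 mmHg is 63% or 87% (D = 5) and 41% or 92% (D = 10), depending on the direction of the imbalance.

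**Step 5: what later adjustment can recover.** With a site term, SE = 10 / √(20p(1 − p)), where p is the letrozole share at one site. At p = 0.5 this is 10 / √5 = 4.47 and power with 17 df is 79.4%. At 6:4 it is 10 / √4.8 = 4.56 and 77.8%; at 7:3, 10 / √4.2 = 4.88 and 72.2%; at 8:2, 10 / √3.2 = 5.59 and 60.5%. Adjustment removes the shift but not the loss of precision; balanced allocation prevents both.

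**The case against.** The strongest reply is that section 4.4 is silent on site. A reader might infer that the plan chose one shared list and decided against stratifying. The documents do not support that: a research pharmacy at each site and a quota of 10 per site fit separate lists equally well, and the web-based assignment fits either. This stands. The finding is that stratification by site is not stated, and the probabilities in the working apply only if a list is shared.

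A reader might also infer that site is ignored throughout, or that the primary test is biased. Neither holds. Site is in the supplementary model. Under an unstratified list the imbalance is random, and the t-test keeps its size over repeated randomisations. The higher error rates arise only given an uneven split, and chance imbalance in any prognostic factor behaves in the same way.

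The likely effect is also modest. About 82% of allocations are 6:4 or better, and a 2 mmHg shift is under half of the 4.47 mmHg standard error. No passage supports any particular D, and both sites use the same seated, room-air blood gas. These points limit how serious the matter is. They do not argue against the change, because the trial is run once and read with the split it gets, and prevention costs almost nothing.

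**Conclusion.** The point holds as a cheap improvement. The plan does not state stratification by site, and its primary test does not use site. If the list is shared, there is a 17.9% chance of a 7:3 or worse split, and between 0.2D (6:4) and 0.6D (8:2) of a site difference in change then enters the primary estimate. The size in mmHg rests wholly on the assumed D: 1 to 4 mmHg at 7:3 for D from 2.5 to 10, with a mean absolute shift of 0.17D over all splits. If per-site blocks are already intended and all patients complete, the shift is zero; what then remains is to state the scheme and bring the primary analysis into line with it. It would go too far to say that the plan rejected site balance, that its test is invalid, or that the result would be systematically biased.

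**What to change.** In section 4.4, state that permuted blocks are stratified by site within the web-based system, with block sizes that complete at 10 per site (giving 5:5) and are kept from site staff.

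In section 8.4.3, make the planned model with baseline and site the primary analysis, with site as a fixed factor. A random-effect variance estimated from two sites rests on 1 degree of freedom. The two changes belong together. Stratifying while keeping the plain t-test makes it conservative if sites differ (type I error 2.8% and power 72% at D = 10, against 79% power with site in the model). Adding site without stratifying leaves the precision loss at uneven splits. The site term also helps when dropout in the completers analysis of section 8.4.5 reopens an imbalance.

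The cost is no extra patients and about 0.3 points of power for the site term (79.7% to 79.4% at 13.2 mmHg with within-site SD 10). That figure does not include the baseline term, which uses one more degree of freedom and may reduce residual variance; the documents give no figure to size this. The remaining work is setting up site strata in the system and amending two sections before randomisation starts.
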